**[name]**  
**Director, Clinical Science International**  
**AtriCure, Inc. (Sponsor)**  
**[name]**  
**[name]**

### FREEZE-AFIB PROTOCOL SYNOPSIS

Regulatory Classification	Post-Market Study
Indication	The AtriCure cryoICE® cryoFORM™ cryoablation probe is indicated for use in the cryosurgical treatment of cardiac arrhythmias by freezing target tissues, creating an inflammatory response (cryonecrosis) that blocks the electrical conduction pathway.
Clinical Investigation Name and Number	FREEZE-AFIB Post-Market Study CP-2021-02
Title	Outcomes of Surgical AF ablation using cryoICE cryoablation system
Objective(s)	
The primary objective of this study is to evaluate the safety and performance of cryoFORM (CRYOF) device.
 
The performance of the device will be demonstrated by establishing that the device effectively eliminates persistent and long-standing persistent atrial fibrillation in a clinically significant proportion of treated patients.

Device(s) Under Investigation	
AtriCure® CryoICE cryoablation system is comprised of:
 
 
• cryoICE® cryoFORM™ cryoablation probe, CRYOF
 
• AtriCure® Cryo Module (ACM1/ACM2)
 

Rationale	
This study is proposed herein is to gather clinical data on the safety and performance of the CRYOF device.
 
Specifically, data from this study will be used for submission to regulatory authorities in Europe, China and other geographies as needed.

Number of Subjects/Sites Required for Inclusion in Clinical Investigation	Up to 150 subjects will be enrolled at up to 20 sites in the US, UK and/or EU.
Clinical Investigation Design	Retrospective-prospective, multi-center, non-randomized, unblinded, post-market study to evaluate the safety and long-term performance of CRYOF during concomitant AF ablation.
Subject Population	Patients who have undergone concomitant surgical AF ablation using the CRYOF device under investigation.
Justification of Sample Size and Performance Goal	Based on a performance goal (PG) of 55%, expected success rate of 68% and attrition rate of 6.5% at the last follow-up visit post procedure, a sample size of 150 patients provides at least 88% power to demonstrate primary performance success. In addition, based on a performance goal of 15% for safety, expected

	
MAE rate of up to 8.5%, the sample size provides 80% power to demonstrate primary safety success.
 
Published literature on the safety and effectiveness of the concomitant AF ablation during cardiac surgical procedure was used to derive the performance criteria for the trial.

Inclusion Criteria	
 
1. Subject is greater than or equal to 18 years of age.
 
2. Subject has documented history of atrial fibrillation.
 
3. Subjects who received surgical ablation for their atrial fibrillation using CRYOF and on whom at least the following lesions were performed: left and right pulmonary vein isolation, roof and floor lines, mitral annulus line, a connecting lesion from left atrial appendage to left pulmonary vein, coronary sinus lesion and LAA exclusion, with a lesion duration of at least 2 minutes.
 
4. Stable subject that underwent non-emergent cardiac surgical procedure(s) on cardiopulmonary bypass including open-heart surgery for one or more of the following: mitral valve repair or replacement, aortic valve repair or replacement, tricuspid valve repair or replacement, or coronary artery bypass procedures, or atrial septal defect (ASD) repair.
 
5. Left Ventricular Ejection Fraction <math>\geq 30\%</math> (determined by echocardiography or cardiac catheterization performed within 90 days of enrollment as documented in patient medical history).
 
6. Subject is willing and able to provide written informed consent.
 
7. Subject is willing and able to return for scheduled follow-up visits.
 

Exclusion Criteria	
 
1. Stand-alone AF without indication(s) for concomitant CABG and/or valve surgery.
 
2. Previous left sided ablation procedures prior to surgical ablation.
 
3. Untreated atrial flutter and symptomatic ventricular arrhythmia.
 
4. Known carotid artery stenosis greater than 80% prior to index ablation procedure.
 
5. Prior history of ischemic stroke or hemorrhagic stroke.
 
6. History of MI with ST elevation within 6 weeks prior to the index ablation
 
7. Documented AF duration of greater than 10 years.
 
8. Large left atrial size i.e., LA diameter <math>>7</math> cm prior to the index ablation procedure.
 
9. Subjects with active systemic infection prior to index ablation procedure.
 
10. Subjects who had documented severe peripheral arterial occlusive disease defined as claudication with minimal exertion prior to the ablation procedure.
 
11. Subjects with history of renal failure requiring dialysis or hepatic failure prior to the ablation procedure.
 
12. A known drug and/or alcohol addiction.
 
13. Mental impairment or other conditions which may not allow the subject to understand the nature, significance, and scope of the study.
 
14. Subjects who are pregnant.
 
15. Subjects who had preoperative need for mechanical circulatory support or intravenous inotropes.
 

	
16. Subjects who are on anti-arrhythmic drug therapy for the treatment of another arrhythmia.
 
17. Subjects in currently undergoing chemotherapy.
 
18. Subjects on long term treatment with oral or injected steroids (not including intermittent use of inhaled steroids for respiratory diseases).
 
19. Subjects who had known connective tissue disorders at the time of index ablation procedure.
 
20. Subjects who had known hypertrophic obstructive cardiomyopathy at the time of index ablation procedure.
 
21. Subjects with known cold agglutinin.
 
22. Subjects who had or tested positive for COVID-19.
 
23. Subjects with bleeding disorders and/or inability to receive anticoagulation
 
24. Subjects undergoing aortic dissection surgery as index procedure.
 
25. Cardiac surgical re-intervention since the index cardiac surgery with concomitant AF ablation procedure.

Subject Follow-up	
Treated subjects will be assessed for primary safety through 30-days post-procedure. Primary performance will be assessed at at least 12-months post-procedure.
 
The minimum follow-up window will be at 12-months, with a maximum follow-up window at 24-months.

Primary Endpoint(s)	
Primary Safety Endpoint:
 
The composite safety endpoint includes surgical ablation procedure related to death, stroke (regardless of level of disability), myocardial infarction, and major bleeding events within 30-days of the index ablation procedure. Deaths beyond 30-days and through last follow up that are attributed to surgical ablation procedure or CRYOF will also be reported as MAEs.
 
The reported events will be adjudicated by an independent physician for severity and relatedness to device and/or procedure.
 
Primary Performance Endpoint:
 
The primary performance endpoint is freedom from any documented atrial fibrillation (AF), atrial flutter (AFL), or atrial tachycardia (AT) lasting >30 seconds in duration at the last follow-up visit in the absence of Class I or III AADs (with the exception of AADs at doses not exceeding those previously failed). The rhythm status used for evaluation of this endpoint will be derived from a 24-hours electrocardiographic rhythm monitoring. The minimum follow-up window is 12 months and maximum at 24 months.
 
Any of the following scenarios will be captured and reported as failure of this effectiveness endpoint:
 
 
• Any electrocardiographically documented AF, AFL or AT recurrences lasting >30 seconds in duration at the last follow-up visit (by 30 second 12-lead ECG or 24-hours continuous ECG monitoring);
 

	
 
• The use of either new Class I or III antiarrhythmic drugs or doses exceeding previously failed (i.e. prior to ablation) at the last follow-up visit;
 
• Any subsequent catheter ablation or surgical ablation treatment for AF, AFL or AT following the index surgical AF ablation procedure (except for treatment of right typical atrial flutter).
 

Secondary Endpoints	
Performance:
 
 
1. Freedom from any documented AF, AFL, or AT lasting >30 seconds at the last follow-up visit regardless of Class I or III AADs.
 
2. Freedom from any documented AF, AFL, or AT lasting >30 seconds at the last follow-up visit in the absence of Class I or III AADs.
 
3. Acute procedural success defined as documentation of sinus rhythm at the end of the procedure.
 
 
Safety:
 
 
1. Implantation of a permanent pacemaker through last follow-up if related to the device or surgical ablation procedure.
 
2. Overall device or surgical ablation procedure related SAEs through last follow up.
 

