## **5.3 Eligibility Criteria**

### **5.3.1 General Eligibility Criteria**

Assessment for general eligibility criteria is based on medical records at the site and interview with a candidate subject. Subjects must meet ALL of the inclusion criteria to be considered for the clinical investigation. If ANY of the exclusion criteria are met, the subject is excluded from the clinical investigation and cannot be enrolled.

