## **6 TREATMENT AND EVALUATION OF ENDPOINTS**

### **6.1 Study Eligibility**

All subjects recruited for study enrollment must meet all study enrollment criteria prior to being enrolled in the study. The clinical investigation site will review all subjects treated with the CRYOF surgical ablation system, and who are within 24-months post-procedure for study eligibility. Once the initial chart review indicates that the subject meets the study inclusion / exclusion criteria, the subject will be approached for their interest in the study, including willingness to return for their follow-up visit.

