### **6.2 Follow-up Assessments**

#### **6.2.1 12-Month Visit ( $\geq$ 12-months but $\leq$ 24-months post index ablation procedure)**

Subjects will be consented 12 to 24 months post procedure and will be provided with a 24-Hour rhythm monitoring device at that time. The post procedure follow-up assessment will include:

- NYHA Classification
- 24-Hr Rhythm Assessment
- Evaluation of AEs/SAEs
- Medications – class I and III AAD's and anticoagulants, including any adjustments
- Review cardioversion since last visit

Note: If a clinical site is capable of remote subject visits, a modified visit assessment may be conducted. Remote subject visits should include Telemedicine appointments with the Investigator, where feasible, to allow direct engagement with the study subject and to ensure complete data collection. Rhythm monitoring devices may be provided to the subject either during an in-clinic follow-up visit, or shipped to the subject for a remote follow-up visit as applicable.

If clinical site is NOT able to perform remote subject visits, an attempt will be made to schedule the study subject visit as close to the visit window as is possible.

Regardless of when the subject is consented, the following data will be collected by reviewing the subjects' medical records retrospectively. For retrospective visits that fall outside of the required windows, please refer to sections 6.2.9 (Unscheduled Visit) and 10.6 (Protocol Deviations).

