## **7 ADVERSE EVENTS**

Safety data for the primary safety endpoint will be collected from the start of the index ablation procedure to 30-days post procedure. The primary safety endpoint will be an evaluation of the incidence of major adverse events (MAEs) listed in section 4.1 for the procedural to 30-day post procedure time period. Deaths beyond 30-days or through last follow-up that are attributed to the surgical ablation procedure or CRYOF would be reported as MAEs.

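### Inclusion 7 and section 6.1 screen on returning for visits although section 6.2.1 allows a remote visit, so an avoidable enrolment gate is applied after the 30-day safety outcome is fixed

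*Combined protocol and SAP*

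**What the plan says.** Inclusion 7, in the synopsis and again in section 5.3.2.1, reads "Subject is willing and able to return for scheduled follow-up visits". Section 5.3.1 makes every criterion binding: "Subjects must meet ALL of the inclusion criteria to be considered for the clinical investigation". Section 6.1 adds a check after chart review: "the subject will be approached for their interest in the study, including willingness to return for their follow-up visit". It names willingness only, not ability.

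Section 6.2.1 describes the single prospective assessment. On timing: "Subjects will be consented 12 to 24 months post procedure and will be provided with a 24-Hour rhythm monitoring device at that time". On format: "If a clinical site is capable of remote subject visits, a modified visit assessment may be conducted". The monitor may be handed over in clinic or "shipped to the subject for a remote follow-up visit as applicable". The schedule of events (6.2.8) lists no 12-lead ECG or echocardiogram at that visit. It lists NYHA class, medications, adverse events, cardioversion review and the 24-hour recording.

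The safety window is much earlier. Section 7 states: "Safety data for the primary safety endpoint will be collected from the start of the index ablation procedure to 30-days post procedure".

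**The concern.** In a trial that enrols before treatment, a requirement to return for visits is routine, because it is judged before any outcome exists. Here every patient has already been treated and is consented at least 12 months after surgery. Ability to travel at that point can be a result of the safety outcome. The composite counts stroke at any level of disability, and stroke is the clearest example of an event that can stop a patient travelling.

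The study has one arm and a fixed performance goal, so no control group loses patients in the same way. If patients with an MAE fail this criterion more often than others, the enrolled MAE rate falls below the rate among all treated patients and the safety test becomes easier to pass. Nothing later in the plan restores them:

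- The random invitation order (3.2) acts before this step.
- The missing-data analyses (8.8) are planned for the study endpoints and do not mention patients who were never enrolled.
- For patients who consent but prove ineligible, section 5.4 captures age, gender, race, screening date and failure reason, but not MAE status.

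**Working it through.** **Reading the sections together.** Inclusion 7 and section 5.3.1 make being able to return a condition of entry. Section 6.2.1 makes returning unnecessary at a capable site. The criterion does not refer to 6.2.1, and 6.2.1 does not refer to the criterion. A patient who can sign consent, wear a shipped monitor and attend by telemedicine can supply the primary performance data, yet on a literal reading fails inclusion 7.

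**Timing.** The safety window closes at day 30. Consent comes at month 12 or later, so at least 11 months separate the two. The rhythm recording is different: the monitor is provided at consent, so that measurement comes after the criterion has been applied.

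**The plan's own figures (section 8.3), by exact binomial.**

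- Safety, pass if at most 15 of 150 have an MAE: P(X ≤ 15 | 150, 0.15) = 0.0493. With 16 allowed it would be 0.081, so 15 is the right limit. Power at 8.5% is 0.794, against 80% stated.
- Performance, pass if at least 89 of 140 respond: P(X ≥ 89 | 140, 0.55) = 0.0247. Power at 68% is 0.887, against more than 88% stated.

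These reproduce. The criterion changes who is counted, not these calculations.

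**Illustration for safety.** All travel fractions are assumptions, since the documents give none. Take a true MAE rate of 15% among treated patients (the null value), 5% of event-free patients unable to travel, and a fraction u of MAE patients unable to travel. Then

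enrolled MAE rate = 0.15(1 − u) / [0.15(1 − u) + 0.85 × 0.95],

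and the chance of a false pass is P(X ≤ 15 | 150, that rate).

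| u | Enrolled MAE rate | Chance of false pass |
|---|---|---|
| 5% (no difference) | 0.1425/0.9500 = 15.0% | 4.9% |
| 6% | 0.1410/0.9485 = 14.9% | 5.4% |
| 7% | 0.1395/0.9470 = 14.7% | 5.9% |
| 10% | 0.1350/0.9425 = 14.3% | 7.7% |
| 15% | 0.1275/0.9350 = 13.6% | 11.6% |

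The decision limit leaves little room. At 15/150, restoring one screened-out MAE patient gives 16/151, with P(X ≤ 16 | 151, 0.15) = 0.076, and the test fails.

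**Illustration for performance.** Take a true responder rate of 55%, 5% of responders lost, and a fraction v of non-responders lost:

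enrolled rate = 0.55 × 0.95 / [0.55 × 0.95 + 0.45(1 − v)].

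- v = 10%: 0.5225/0.9275 = 56.3%, and the chance of passing rises from 2.5% to 5.0%.
- v = 3%: 0.5225/0.9590 = 54.5%, and it falls to 1.8%.

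The sign depends on which group attends less, and the documents do not say.

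**The case against.** The strongest reply is that a site need not read inclusion 7 literally. Section 6.2.1 itself calls the remote contact a visit, and section 6.2.7 accepts remote evaluation of symptoms. A site could treat a patient who will complete a remote visit as eligible. That is fair, so it cannot be said that such patients will necessarily be screen-failed. But no section says that a remote visit satisfies the criterion, and up to 20 sites may decide differently. The lenient reading also does not help where a site cannot do remote visits.

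The second reply is that inclusion 7 is only part of the selection. Sections 3.1 and 5.2.1 already list death, major morbidity such as stroke, and inability to consent as screen-failure reasons, and inclusion 6 requires written consent. Many patients with severe stroke would be lost by those routes whatever inclusion 7 said. This stands.

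The third concerns size. The MAE list includes transfused bleeding, TIA and death. Death cannot act through ability to travel, TIA resolves within 24 hours by definition, and many bleeds would not prevent travel a year later. A reader might be tempted by a larger contrast: with 25% of MAE patients unable to travel against 5% of others, the false-pass chance would be 24.4%. Nothing in the documents supports a five-fold difference.

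Finally, a reader might infer that the criterion also tilts the performance test towards success, on the view that patients with recurrent arrhythmia stay away. The documents do not support that. The recording is made after consent, and symptomatic patients could be more motivated to attend.

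**Conclusion.** The point holds as an unreconciled eligibility rule with a likely bias in one direction for safety. Inclusion 7 and section 6.1 do not acknowledge the remote route in section 6.2.1, and they are applied after the 30-day outcome is fixed. Read literally, they exclude living, consenting patients who could complete the assessment from home, and sites may differ in how they read them.

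The size is unknown. Within the illustrative range, the false-pass chance for safety goes from 4.9% to between 5.4% and 11.6%. This assumes a true MAE rate of 15%, 5% of event-free patients unable to travel, 6% to 15% of MAE patients unable to travel, and no use of the remote route for them. Any use of that route makes the effect smaller. No direction can be claimed for performance.

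This is one avoidable part of a wider selection after the outcome. It should be corrected because the protocol already contains the means, not because it has been shown to decide the result.

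**What to change.** Reword inclusion 7 in the synopsis and in section 5.3.2.1 to: *willing and able to complete the follow-up assessment, in clinic or remotely as allowed in 6.2.1*. Change section 6.1 to: *willingness to complete the follow-up assessment*. At sites without remote capability, record *unable to travel* as a separate screen-failure reason in the existing EDC log, and report the count. The log's list of reasons is already open-ended, so this adds a category rather than a new procedure.

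The cost is a wording amendment and one log category. Endpoints, sample size and tests are unchanged. The small downside is more remote visits, which section 6.2.1 already accepts. The change does not recover patients lost through death, inability to consent or major morbidity, and the report should say so.

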**COMPLIANCE STATEMENT**

This clinical investigation will be conducted in accordance with this Clinical Investigation Plan, the Declaration of Helsinki, applicable Good Clinical Practices and regulations (e.g., US 21 CFR Part 50, 21 CFR Part 56, 21 CFR Part 812 and OUS ISO14155:2020) and the appropriate local legislation(s). The most stringent requirements, guidelines or regulations must always be followed. The conduct of the clinical investigation will be approved by the appropriate Institutional Review Board (IRB)/Ethics Committee (EC) of the respective investigational site and by the applicable regulatory authorities.

This clinical investigation will be financed by AtriCure. Investigational sites will be compensated by AtriCure for participation in the clinical investigation per the conditions of agreement between the Sponsor and the Investigational site.

## **1 INTRODUCTION**

This clinical investigation will be conducted in accordance with this Clinical Investigational Plan (CIP), also referred to herein as the “Protocol”. All investigators involved in the conduct of the clinical investigation will be qualified by education, training, or experience to perform their tasks and the training will be documented appropriately. The investigator will create and maintain source documents throughout the clinical investigation and make them available as requested during monitoring visits or audits, as well as maintain documentation of the type and location of these source documents. The investigator will also determine the cause and implement appropriate corrective and preventative actions to address any significant noncompliance.

### **1.1 Background and Rationale**

#### **1.1.1 Background**

Atrial Fibrillation (AF) is characterized by very fast, irregular beating of the heart's upper chambers (the atria). It occurs when normal sinus rhythm is disrupted by errant irregular electrical signals in the atria. These erratic electrical propagation patterns disrupt the regular pumping action of the atria, preventing complete filling of the ventricles, and causing irregular beating of the ventricles. These spasms often lead to regions of static blood flow in the atria and consequently, blood clot formation, stroke and even death. It is estimated that AF is responsible for 15% - 25% of all strokes. Symptoms of AF typically include a rapid and irregular heartbeat, palpitations, dyspnea, discomfort, dizziness and fatigue.

Atrial fibrillation (AF) is a common heart arrhythmia that carries a significant mortality and morbidity risk and is associated with three primary clinical sequelae: loss of atrial transport, loss of regular cardiac chamber synchronization, rhythm & rate response, and thromboembolism. Up to a third of all patients with symptomatic long-standing persistent AF will experience at least one embolic episode during the course of their atrial fibrillation. Lone AF (e.g. no structural heart disease) with no left atrial enlargement may be categorized as a benign disease since it is not associated with an increase in mortality or complications than that of the general population. However, AF patients, especially those with enlarged atria or structural heart disease, are at an increased risk of congestive heart failure, thromboembolic events, and mortality. In fact, permanent AF (long-standing persistent AF after the decision not to treat) is associated with 8.2% annual all-cause mortality, 5.1% annual thromboembolic event rate, 2.7% annual major bleeding rate, and 16.6% annual heart failure rate.ii

The underlying theory surrounding the source of irregular conduction pathways in patients with atrial fibrillation involves ectopic electrical activity or micro-reentrant circuits that can originate from specific locations in the heart such as the pulmonary vein orifice in patients with lone AF (focal), or more commonly associated with the reentry of conduction circuits throughout the atria in patients with structural remodeling (wavelet AF).

Only 12% of patients have Lone AF, leaving the remaining 88% with some form of structural heart disease.iii This structural heart disease commonly includes hypertension, coronary artery and valvular heart disease. Left untreated, AF can lead to ventricular dysfunction, atrial dysfunction, left atrial enlargement thus perpetuating the structural remodeling that causes and worsens atrial fibrillation and heart failure.iv

The relationship between progressive structural remodeling and atrial fibrillation explains why 88% of AF patients are persistent or permanent leaving only 12% as paroxysmal.v Furthermore, 76% of AF patients either have enlarged atria with diameter greater than 4.5 cm or an increase in left ventricular thickness.vi Atrial enlargement, as well as structural remodeling, determines the

incidence of atrial fibrillation and whether AF patients observe complications throughout their lifetime.

Patients newly diagnosed with AF are medically managed with multiple courses of antiarrhythmic drugs (AAD), and anticoagulants to lessen the risk of thromboembolic accidents. Within 5 years, most patients will become refractory to AADs, and will require additional intervention. Often AADs will have the effect of “dumbing down” the heart’s natural pacemaker, necessitating the need for permanent rate control. Although the risk of thromboembolism is reduced in the presence of anticoagulation, it is still substantially higher than that observed in the general population. In addition, bleeding complications from anticoagulation regimens occur at a cumulative rate of 1% per year.

